#### **9.4 Study Pause Procedure**

The PSRT will be notified immediately by Emmes if they ascertain that a pause rule has been met. If a site investigator or the PSRT first become aware that a pause rule has been met, they will inform Emmes immediately. Emmes will cease randomization and notify the site PIs that a pause rule has been met and that no further enrollment should occur, and no study vaccines are to be administered until specific notification is provided that study vaccinations can resume.

As soon as it is confirmed that a study pause rule has been met, the IDMC will be notified and will expeditiously (within 48 hours, if possible) convene by teleconference to review all available, relevant information, including initial exclusive access to unblinded data. The IDMC reviews will be summarized with recommendations to PATH as to whether there are safety concerns and whether the study should continue without change, be modified, or be stopped.

If at any time, a decision is made to permanently discontinue administration of study vaccine in all participants, notification will be provided by PATH to the NRA and by the PI to the IRB/IEC within 48 hours.

If PATH re-starts the study after IDMC review and recommendation, enrollment and study vaccination may resume. The PIs will report the study pause and decision to resume to their IRB/IEC.

## **10 DATA HANDLING and RECORDKEEPING**

The investigator is responsible for assuring that the data collected are complete, legible, attributable, accurate, and recorded in a timely manner. Data collection is the responsibility of the site clinical trial staff under the supervision of the site PI. All source documents and laboratory reports must be reviewed by the clinical team and data entry staff, who will ensure that they are accurate and complete.

Emmes is responsible, under oversight of PATH, for data management activities, including quality review, analysis, and reporting of the study data according to Standard Operating Procedures (SOPs).

### **10.1 Definitions**

#### **10.1.1 Source Data**

All information in original records and certified copies of original records or clinical findings, observations, or other activities in a clinical trial necessary for the reconstruction and evaluation of the trial. Source data are contained in source documents (original records or certified copies; ICH E6[R2] section 1.51).

### **10.1.2 Source Documents**

Original documents, data and records (e.g., hospital records, clinical and office charts, laboratory notes, memoranda, participants' diaries of evaluation checklists, pharmacy dispensing records, recorded data from automated instruments, copies or transcriptions certified after verification as being accurate and complete, microfiches, photographic negatives, microfilm or magnetic media, x-rays, participant files, and records kept at the pharmacy, at the laboratories, and at medico-technical departments involved in the clinical trial (ICH E6[R2] section 1.52).

## **10.2 Data Capture Methods (Case Report Form Development and Completion)**

The clinical data in source documents will be entered directly into a 21 CFR Part 11-compliant EDC system by trained and qualified study staff. The electronic CRF (eCRF) for the EDC system will be developed by the Emmes data management center with input from study staff and approval of PATH. Clinical data for each participant will be entered directly into the eCRF from the source documents.

It is the site PIs' responsibility to ensure the accuracy, completeness, and timeliness of the data reported in the participant's eCRF and any supporting documentation. All source documents should be completed in a neat, legible manner to ensure accurate interpretation of data. Source documentation supporting the eCRF data should document the dates and details of study procedures, AEs and participant status. The site PIs/institutions will maintain all information in the eCRFs and all source documents that support the data collected from each participant in a secure area and treated as confidential material.

## **10.3 Data Management**

A thorough Data Management Plan and corresponding database compliant with ICH requirements will be developed by Emmes Data Management (DM). Emmes DM will build, validate, and maintain a Good Clinical Practice (GCP) compliant EDC system. The data system will include password protection and internal quality checks, such as automatic range checks, to identify data that appear inconsistent, incomplete, or inaccurate. Write access to the system will be limited to authorized Investigators and study staff, and the system will automatically keep an audit trail of all entries and corrections in the eCRF.

Emmes DM will perform all activities as per their SOPs, and in accordance with PATH SOPs. Coding of medical history and adverse events will be performed using the latest version of MedDRA. Medications will be coded using the latest World Health Organization Drug Dictionary. The eCRFs and any supporting documentation should be available for retrieval or review at any given time.

## **10.4 Retention of Study Records**

The site PIs are responsible for retaining study records for a period of 2 years following the date that a marketing application is approved for the product or, if no application is to be filed or, if a file application is not approved, until 2 years after the investigation is discontinued and the NRA is notified. PATH will be responsible for providing the site with date of vaccine approval or IND/regulatory withdrawal. No records will be destroyed without the written consent of PATH. PATH will notify the investigator in writing when the trial related records are no longer needed.

These records are also to be maintained in compliance with local IRB/IEC and local authority medical records retention requirements, whichever is longest. Storage of all trial-related documents will be such that confidentiality will be strictly maintained to the extent provided by local law.

## 11 STATISTICAL CONSIDERATIONS

This section summarizes the primary features of the statistical analysis for the study. A statistical analysis plan (SAP) will be prepared and finalized prior to database lock and will specify all analyses to be performed. Emmes will author the SAP and produce the statistical analysis, under the guidance and oversight of PATH.

### 11.1 Overview and General Design

This multicenter trial is the first-in-human assessment of these novel oral poliomyelitis vaccines. It will be an 8-arm, randomized, observer-blind, controlled trial, with Sabin monovalent vaccines serving as the control for each novel type (see study schema in Section 3). Within each cohort and according to prior vaccination status (exclusively IPV or OPV-containing), healthy, adult participants will be randomized into the study arms receiving mOPV1 or nOPV1 (cohorts 1 and 2, 115 participants), and once each of those cohorts are completely accrued, participants will be randomized into the corresponding type-specific cohorts receiving mOPV3 or nOPV3 (cohorts 3 and 4, 115 participants) in the same manner.

### 11.2 Randomization Procedures

Within cohorts 1 and 3, participants with exclusively IPV prior vaccination will be randomized 1:1 to nOPV vs mOPV with all participants receiving a single dose, and within cohorts 2 and 4, previously OPV-vaccinated participants will be randomized 2:1 to nOPV vs mOPV, with all participants receiving 2 doses, with the second dose 28 days following the first dose. Block randomization will be stratified by site to ensure balance within each site, without a prespecified number to be enrolled at each site. The randomization scheme will be generated and maintained by Emmes. Participants will be randomized using the Emmes IWRS. Any enrolled participant who is randomized but withdraws for any reason prior to vaccination will be replaced.

The site pharmacists with primary responsibility for dispensing study vaccines are charged with maintaining security of the treatment assignments.

### 11.3 Sample Size

The sample sizes chosen for this study are chosen primarily to enable evaluation of safety in a sufficient number of adults prior to a subsequent study phase in younger individuals, to provide an opportunity to demonstrate an immune response with study vaccination, and to enable collection of stool samples to permit a preliminary evaluation of genetic stability of shed virus. Definitive evaluations of immunogenicity, viral shedding, and genetic stability are planned for future study phases.

#### *Primary Safety Evaluation*

For the safety endpoints, the table below describes the probability of detection of rare events and the precision afforded by the sample sizes used in this study. These levels are consistent with standard phase 1 vaccine studies aimed at safety evaluation and provide adequate ability to detect unexpected adverse events prior to age de-escalation in a subsequent study.

Sample size	Minimum AE rate producing 95% probability of observation with given sample size (%)	95% Confidence interval for event rate if 0 events are observed	95% Confidence interval for event rate if 1 event is observed
15	18.2	(0.0, 21.8)	(0.1, 31.9)

20	13.9	(0.0, 16.8)	(0.1, 24.9)
25	11.3	(0.0, 13.7)	(0.1, 20.4)
50	5.8	(0.0, 7.1)	(0.1, 10.6)
70	4.2	(0.0, 5.1)	(0.04, 7.7)

*Minimum adverse event rates required to have ≥95% probability of detecting at least one such event with given sample sizes, along with two-sided 95% exact confidence intervals if 0 or 1 events are observed.*

### *Immunogenicity Evaluation*

[figure not shown]
Assessment of immunogenicity is a secondary objective in this study. Due to the prior vaccinations received by those to be enrolled into the study, baseline immunity (titer of type-specific neutralizing antibody) to poliovirus types 1 and 3 is expected to be high, with the level boosted by study vaccination. While it is expected that the presence of an immune response can be observed by an increase in neutralizing antibody titer following vaccination, and because the post-vaccination immunity is anticipated to exceed the assay upper limit of quantification (ULOQ) for some participants, definitive comparisons of study vaccination groups to the relevant control (nOPV vs type-specific control, within cohort according to prior vaccination [exclusively IPV vs OPV-containing]) will not be possible within this phase 1 study. Evaluation of immunogenicity, therefore, will be primarily descriptive in nature; comparisons to the relevant control will be made, but the sample size is not based on achieving a specific level of statistical power for these comparisons. Comparative evaluation for immunogenicity will focus on the cohorts previously receiving OPV vaccinations but will also be conducted among exclusively IPV-vaccinated participants.

Prior studies of type 2 in OPV-vaccinated adult populations indicate baseline immunity within the quantifiable range, with mean  $\log_2$  neutralizing antibody (NAb) titers ranging from 7.8 to 8.8 (unpublished data), and with the majority of participants achieving NAb titer >ULOQ 28 days following a single dose of a Sabin-2 vaccine as well as investigational type 2 vaccines. Using a regression model permitting censoring at assay lower limit of quantification (LLOQ) and ULOQ, the standard deviation (SD) of post-vaccination NAb titers is estimated to be in the range of 3 – 3.5 on the  $\log_2$  scale, which is consistent with other published data for type 1 (prior to a boost vaccination in adulthood) [11]. In the study involving type 2, the post-vaccination GMT ratio (candidate/control) and its corresponding CI were able to be estimated; similar methods will be employed here (see below). With respect to binary immune response endpoints (seroconversion, other seroresponse rates), data from the type 2 study indicate seroconversion rates ranging from approximately 30% to 75%, depending on the vaccine and potency level administered. Rates of a minimum 2-fold response ranged from approximately 50% to 75%, with rates of any fold-rise ranging from approximately 60% to 85%.

Using these values, simulation studies were conducted to evaluate the precision of estimates of the GMT, GMT ratio, response rates, and differences in response rates, assuming that 48 and 24 of the 50 and 25 or 28 and 14 of the 30 and 15 prior OPV participants randomized to receive nOPV or mOPV, respectively, provide samples for analysis. The figure below displays the average half-width of the two-sided 95% confidence intervals for the four evaluations across the range of relevant inputs ( $\log_2$  NAb SD for GMts, true rate for the various response rates). The level of precision expected to be available, described within the figures, is considered adequate to determine if there is sufficient evidence of an immune response to warrant progressing into populations where the immune response may be more thoroughly described and compared.

The figure indicates, for example, that if the SD of the  $\log_2$  post-baseline serum NAbs is 3.0 and both candidate and control vaccines are equally immunogenic, then one can expect, on average, that the CI for the difference in mean  $\log_2$  NAbs will be approximately (-1.48, 1.48) with 48:24 or (-1.92, 1.92) with 28:14 when the estimated difference is 0 (ratio = 1), providing high confidence that the actual absolute  $\log_2$  difference is <2 (ratio <4). If instead the SD is 2.0, the CI would be approximately (-0.97, 0.97) with 48:24, providing confidence that the actual absolute difference is <1 (ratio <2). For the lower sample size, with an SD of 2.0, the CI would be approximately (-1.25, 1.25), providing high confidence that the actual absolute  $\log_2$  difference is <1.58 (ratio <3). For the candidate vaccine group alone, assuming a SD just less than 3.5 and 48 evaluable subjects, the CI for the mean  $\log_2$  titer would be approximately  $\pm 1.0 \log_2$ . That is, if the estimated GMT is  $2^8$  (256), the figure indicates the CI would be expected to be approximately ( $2^7$ ,  $2^9$ ), or equivalently (128, 512), on average. If instead the SD is 2.5 with 48 evaluable subjects, the CI would be expected to be approximately ( $2^{7.3}$ ,  $2^{8.7}$ ), or equivalently (158, 416), on average.

With respect to response rates, for which precision is naturally lower than the continuous measurement of serum NAbs: if a true response rate is 50% in each group (maximum variability), then the CI for the estimated candidate vaccine response rate would be expected to average  $\pm 15\%$  ( $\pm 20\%$  for 28 evaluable subjects) from the point estimate, and the CI for the difference in response rates would be expected to average  $\pm 23\%$  ( $\pm 30\%$  for 28:14) from the point estimate.

### *Intestinal Immunity, Genetic Stability*

In recognition that previously OPV-vaccinated participants are unlikely to shed vaccine virus in substantial quantities, the 30-40 participants for each type with exclusive prior IPV vaccination to be randomized 1:1 to nOPV or mOPV are included primarily to provide a preliminary indication of intestinal take (shedding of virus, indicating replicating infection), as well as to provide samples for potential genetic stability analysis of shed virus, including NGS and evaluation in a mouse neurovirulence assay. The relevant

neurovirulence assay for comparison to Sabin-strain vaccines is yet to be developed, but it is anticipated that a null hypothesis of no difference, vs. an alternative hypothesis of superiority of nOPV to mOPV will be evaluated from this model; a defined level of statistical power is not a requirement for this preliminary evaluation. It is currently unknown what levels of paralysis may be seen in transgenic mice in such an assay as assay development is ongoing but based on preclinical data indicating no paralysis associated with passaged candidate vaccine virus, and the known reversion to neurovirulence resulting in frequent paralysis of mice inoculated with reverted Sabin-strain vaccines, sufficient discriminatory capability is expected to be provided by 15-20 participants per vaccine.

## **11.4 Definitions of Populations to be Analyzed**

### **11.4.1 Enrolled Population**

The Enrolled Population is defined as all participants who provide informed consent, regardless of the participant's randomization and treatment status in the study.

### **11.4.2 Safety Population**

The Safety Population is defined as all participants in the Enrolled Population who received a study vaccine.

### **11.4.3 Full Analysis Population**

The Full Analysis Population (FAP) is defined as all participants in the Enrolled Population who were randomized, received a study vaccination, and provided a baseline and at least one post-study vaccination evaluable serum sample.

### **11.4.4 Per-Protocol Population**

The Per-Protocol (PP) population is defined as all participants in the FAP who correctly received all study vaccinations per randomization with no major protocol deviations that are determined to potentially interfere with the immunogenicity result of the participant. The PP population will be defined on the time-point level; that is, a participant may be evaluable in the PP population with their baseline and Day 29 samples, but not for the Day 57 sample due to a major protocol deviation. For summaries of the PP population on the participant level, the PP membership for the Day 29 visit will be used.

Prior to database lock, the database will be searched for potentially disqualifying deviations. Additionally, protocol deviations will be collected from monitoring and medication listings will be reviewed; this information will be reviewed in a Data Review Meeting (DRM) attended by representatives from PATH, Emmes, and the study sites to determine PP population eligibility. Efforts will be taken to blind participant group membership during this review to the extent possible in this observer-blind study. The following constitute potential criteria for elimination from the per-protocol population. The list is not exhaustive, as unexpected deviations may arise requiring unique consideration.

- Missed vaccinations
- Significant non-compliance with visit windows
- Any eligibility criteria not met
- Receipt of a non-study vaccine
- Receipt of immunosuppressants or immune modulators
- Receipt of study vaccine not stored as per manufacturers approved storage condition
- Incomplete vaccine dose administration or vomiting within 5 minutes of vaccination

- Serological results unavailability
- Wrong randomization
- Dosed with wrong treatment arm

A DRM report will provide the criteria used for determination, as well as list the participants excluded and accompanying rationale.

#### **11.4.5 Other Populations**

The SAP will define additional subgroup participant populations for specific analyses.

### **11.5 Analytical Methodology**

#### **11.5.1 Descriptive Methodology**

All data collected will be summarized and/or listed. Analyses will be performed using SAS® software (SAS Institute Inc., Cary, NC, USA) version 9.4 or higher.

Unless otherwise specified, descriptive statistics include the mean, SD, median, minimum, maximum for continuous variables, and the number and proportion in each group for categorical variables. Unless otherwise specified here or in the SAP, statistical tests, and confidence intervals (CIs) will be computed using a two-sided 5% significance level. Exact (Clopper-Pearson) CIs will be used for univariate summaries of dichotomous variables, and Miettinen-Nurminen score-based confidence intervals will be used for rate differences. All proportions will use as denominator the number of participants contributing data at the specified time point within the specified group and study population.

Summaries will be presented by group and by time point, where relevant.

For all summaries outlined below, the SAP will contain additional detailed description of the analyses to be conducted.

#### **11.5.2 Analysis Sequence**

Analysis of immunological endpoints will occur separately for each type, in advance of the completion of long-term safety follow-up of participants. Following database lock for long-term safety follow-up and completion of stool viral shedding assays, a complete final analysis will be produced and incorporated into the clinical study report (CSR).

#### **11.5.3 Changes in Analysis Plan**

Any deviations or changes from the statistical analyses specified in the protocol will be described and justified in the SAP and the CSR.

#### **11.5.4 Baseline and Demographic Characteristics, and Participant Disposition**

Descriptive statistics will be computed for demographic (e.g., height, weight, race, sex) characteristics in both the safety and PP populations, and other initial participant characteristics (e.g., medical and surgical history, concomitant diseases) in the safety population.

Concomitant medications will be coded using the WHO Drug Dictionary. Medical history will be coded using the most recent version of the Medical Dictionary for Regulatory Activities (MedDRA).

Participant disposition including dropout and reasons for dropout, as well as study population membership will be summarized descriptively, and supported with a CONSORT (Consolidated Standards of Reporting Trials) diagram.

Screening serology will be summarized descriptively, including HIV, HBV, and HCV, pregnancy testing, and type-specific anti-polio antibodies among all participants, and in the enrolled population.

### **11.5.5 Safety Analysis**

All safety analyses will be conducted in the safety population. Summaries will be computed separately by group, and within type across group (i.e., combined Groups 1 and 3 compared to combined Groups 2 and 4, and combined Groups 5 and 7 compared to combined Groups 6 and 8).

The extent of exposure will be summarized by tabulating the number of doses of a given vaccine received for each participant, as well as descriptive summaries of the time (days) between vaccinations

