### 3 STUDY DESIGN

This multicenter trial is the first-in-human assessment of these novel oral poliomyelitis vaccines. It will be an 8-arm, randomized, observer-blind, controlled trial, with Sabin monovalent vaccines serving as the control for each type (see study schema, below). 150 to 230 healthy, adult participants will be recruited. 30 to 40 of 60 to 80 participants with an exclusive IPV prior vaccination history (cohort 1) will be randomized in a 1:1 ratio to study groups 1 and 2 and allocated to receive nOPV1 or mOPV1, and once these study arms are completely accrued, the other 30 to 40 exclusively-IPV vaccinated participants (cohort 3) will be randomized in a 1:1 ratio to study groups 5 and 6 and allocated to receive nOPV3 or mOPV3.

In parallel, 45 to 75 of 150 participants with an OPV-containing prior vaccination history (cohort 2) will be randomized in a 2:1 ratio to study groups 3 and 4 and allocated to receive two doses of nOPV1 or mOPV1, respectively, and once these study arms are completely accrued, the other 45 to 75 participants with an OPV-containing prior vaccination history (cohort 4) will be randomized in a 2:1 ratio to study groups 7 and 8 and allocated to receive two doses of nOPV3 or mOPV3, respectively.

Participants assigned to two doses of vaccine will receive the second dose 28 days following the first dose. Initial vaccination for Cohorts 1 and 2 participants will be limited to no more than 5 participants per day and a total of 10 participants during the first week of vaccination. Participants will be followed until 24 weeks after their Day 1 study vaccination.

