#### **11.5.5.2 Unsolicited Adverse Events**

All unsolicited adverse events will be listed and summarized in tables. Unless an AE is classified as an SAE, summaries of unsolicited AEs will be made using only those events recorded with onset within 28 days of the prior vaccine dose. Unsolicited adverse events will primarily be summarized on the participant level, where a participant contributes once to a given event type under the maximum severity and/or causality, as appropriate. Tables will additionally display the number of events of a given type observed within a group, regardless of the number of participants from which they originate.

Unsolicited adverse events will be summarized by severity and by relationship; SAEs will be summarized overall, and by reason for seriousness designation. In addition, all AEs, coded with MedDRA, will be summarized by System Organ Class (SOC) and Preferred Term (PT), and separate tables by SOC and PT will be prepared for severe unsolicited AEs, severe AEs, related AEs, severe related AEs, and SAEs. A table will be prepared summarizing all preferred terms occurring in  $\geq 2\%$  of participants. Additional summaries will include the rate of participants experiencing an AE leading to withdrawal from vaccinations, or from the study. Additional listings will be prepared for severe AEs, related AEs, and SAEs. Within OPV type, the rates of participants experiencing severe adverse events, related adverse events, and serious adverse events will be compared across groups using a two-sided Fisher's exact test for pairwise comparisons.

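### The pooled nOPV-versus-mOPV safety comparison ignores cohort, although cohort fixes the allocation ratio, the number of doses and the priming history

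*Protocol*

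**What the plan says.** Section 11.5.5 asks for safety summaries by group and also within type across groups, with "combined Groups 1 and 3 compared to combined Groups 2 and 4, and combined Groups 5 and 7 compared to combined Groups 6 and 8". It mentions no stratification or adjustment for cohort, and it attaches no test or interval to the pooled arms.

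Section 11.2 sets the allocation. In cohorts 1 and 3, "participants with exclusively IPV prior vaccination will be randomized 1:1 to nOPV vs mOPV with all participants receiving a single dose". In cohorts 2 and 4, "previously OPV-vaccinated participants will be randomized 2:1 to nOPV vs mOPV, with all participants receiving 2 doses". Section 3 gives the sizes for type 1: "30 to 40 of 60 to 80 participants with an exclusive IPV prior vaccination history (cohort 1) will be randomized in a 1:1 ratio", and "45 to 75 of 150 participants with an OPV-containing prior vaccination history (cohort 2) will be randomized in a 2:1 ratio". Type 3 has the same structure.

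The tests are worded differently in neighbouring sections. Section 11.5.5.1 places the Fisher tests for solicited events within cohort, by dose and across doses. Section 11.5.5.2 says that the rates of severe, related and serious adverse events "will be compared across groups using a two-sided Fisher's exact test for pairwise comparisons". It limits this to one poliovirus type but does not name cohort.

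**The concern.** Randomisation took place within cohort, at different ratios. When the two cohorts of a type are added together, the nOPV and mOPV arms no longer have the same mix, so the crude contrast is not the randomised one. The mix differs in two ways that can affect adverse event risk: number of doses (and so length of collection) and prior vaccination.

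Safety is the only primary objective, and the pooled arms give the largest numbers per vaccine. A few points of difference produced by the design could be read as a vaccine effect, or could hide one, in first-in-human data meant to support the move to children.

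The protocol respects cohort elsewhere: in the solicited-event tests (11.5.5.1), the immunogenicity comparisons (11.5.6.2) and the shedding comparisons (11.5.7.2). Only the pooled safety contrast and the wording of 11.5.5.2 drop it.

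**Working it through.** **The plan's own figure.** The n = 70 row of the safety table in 11.3 equals the pooled nOPV arm of one type at maximum enrolment (20 + 50). The minimum rate is 1 - 0.05^(1/70) = 4.19% (stated 4.2). The exact upper limit with 0 events is 1 - 0.025^(1/70) = 5.13% (stated 5.1), and with 1 event the interval is 0.04% to 7.70% (stated 0.04, 7.7). The row reproduces.

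**Inputs per type** (study schema in section 3; 11.2)
- Maximum: IPV one dose, 20 nOPV and 20 mOPV; OPV two doses, 50 nOPV and 25 mOPV.
- Minimum: IPV 15 and 15; OPV 30 and 15.
- Unsolicited events are collected for 28 days after each dose (8.2).
- Adverse event rates by cohort are not given; those below are assumptions. All participants are taken to receive their scheduled doses.

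**Make-up of the pooled arms**
- Two-dose share, maximum: 50/70 = 71.4% against 25/45 = 55.6%. Minimum: 30/45 = 66.7% against 15/30 = 50.0%.
- Doses per participant: 1.71 against 1.56 (maximum); 1.67 against 1.50 (minimum).
- Mean unsolicited window, maximum: (20×28 + 50×56)/70 = 48.0 days against (20×28 + 25×56)/45 = 43.6 days. Minimum: 46.7 against 42.0 days.

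**Expected crude difference with no vaccine effect.** Let p_IPV and p_OPV be the cohort risks, the same for both vaccines within a cohort, and let w be the two-dose share. Then

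difference = (w_nOPV - w_mOPV) × (p_OPV - p_IPV).

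The factor is 50/70 - 25/45 = 0.159 at maximum and 30/45 - 15/30 = 0.167 at minimum. If one cohort fills to its maximum and the other to its minimum, it is 50/65 - 25/40 = 0.144 or 30/50 - 15/35 = 0.171.

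Example (30% IPV, 51% OPV, which is two independent doses at 30% each), maximum: nOPV (20×0.30 + 50×0.51)/70 = 45.0%; mOPV (20×0.30 + 25×0.51)/45 = 41.7%; difference +3.3 points.

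The last column is the exact type I error that an unstratified two-sided 5% Fisher test would have if it were applied to the pooled arms.

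| Assumed risk, IPV / OPV | Difference in points, max (min) | Fisher type I error in %, max (min) |
|---|---|---|
| 5% / 9.75% | +0.75 (+0.79) | 3.25 (1.98) |
| 10% / 19% | +1.43 (+1.50) | 3.95 (3.44) |
| 30% / 51% | +3.33 (+3.50) | 4.47 (3.65) |
| 30% / 30% | 0 (0) | 3.96 (3.58) |
| 30% / 10% | -3.17 (-3.33) | 4.92 (4.09) |
| 50% / 20% | -4.76 (-5.00) | 6.06 (4.39) |
| 10% / 50% | +6.35 (+6.67) | 7.18 (4.82) |
| 20% / 80% | +9.52 (+10.00) | 9.80 (5.55) |

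**With stratification.** The expected difference inside each cohort is 0, so any weighted mean of the two cohort differences is also 0, for every pair of rates.

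**Pairs allowed by 11.5.5.2.** Four groups within a type give 6 pairs. Only two of them (1v2 and 3v4 for type 1; 5v6 and 7v8 for type 3) are randomised comparisons.

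**The case against.** The strongest reply is that 11.5.5 is about summaries. It names no test for the pooled arms and also plans results by group. The solicited-event tests are already within cohort and by dose. In 11.5.5.2 the word group may simply mean the numbered arms, and a test of Group 1 against 2, or 3 against 4, pools nothing. The endpoints tested there may also be rare: section 1.5.1 describes severe events with the parent nOPV2 candidate as infrequent and reports no vaccine-related SAE. At assumed rates of 2% and 4% the bias is about 0.3 points. Analysis detail may also be left to the SAP.

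Most of this stands as a limit on reach and size. A reader might infer that the plan specifies a Fisher test on the pooled arms, or that the solicited-event tests are confounded. The text supports neither: 11.5.5.2 is ambiguous, and 11.5.5.1 excludes the second.

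It does not remove the point. Section 11.5.5 itself sets one pooled arm against the other, and a reader of such a table will take the difference as a comparison of vaccines. The protocol states this contrast, and 11.5.3 requires departures from it to be justified, so it is more than detail left to the SAP. The wording of 11.5.5.2 also allows pooled arms or non-randomised pairs, unlike the section just before it.

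**Conclusion.** The point holds, confined to the pooled contrast in 11.5.5 and the loosely worded Fisher tests in 11.5.5.2. The difference in mix is certain from the design. The resulting bias depends on cohort risks that the protocol does not give: about 1 to 4 points in either direction at moderate assumed rates, under 1 point for rare events, and none if the cohorts have equal risk.

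A reader might infer a bias against nOPV because that arm has more doses per participant. The documents do not establish this. Section 11.3 expects OPV-primed participants to shed little; if they also react less, the sign reverses.

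A reader might also infer a broad inflation of false positives. If a pooled Fisher test were run, its error would stay below 5% in the moderate cases and exceed it only when cohort rates differ widely. The harm is mainly a biased estimate.

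For SAEs, collection runs to Day 169 for everyone, so the imbalance is in doses and priming, not in follow-up time.

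**What to change.** - In 11.5.5, keep the crude pooled counts as descriptive only. Make any pooled nOPV-versus-mOPV safety comparison stratified by cohort: a Mantel-Haenszel or stratified Miettinen-Nurminen risk difference, with a stratified exact test if a test is wanted.
- In 11.5.5.2, restrict the Fisher tests to the randomised pairs 1v2, 3v4, 5v6 and 7v8. This matches the within-cohort rule in 11.5.5.1, 11.5.6.2 and 11.5.7.2.
- Restricting a pooled table to the period after dose 1 would equalise exposure but not priming, so it does not replace stratification.

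The cost is a few lines of text and standard software options. No new data and no change to enrolment are needed.
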